**Palatal Wound Healing Evaluation After
Application of Platelet Rich Fibrin Versus 0.2%
Hyaluronic Acid Dressings
(Randomized Controlled Clinical Trial)**

Methodology

Date: 12/5/2020

Sample selection and assignment:

Thirty patients (16 females and 14 males) who were candidates for free gingival grafting surgery participated in this prospective clinical trial.

The subject were recruited consecutively from the outpatient clinic of Oral Medicine, Periodontology, oral Diagnosis and Radiology Department, Faculty of Dentistry, Ain Shams University .The purpose of the study was explained to all patients and an informed consent was signed before the conduction of the study. The proposal was presented to the faculty of Dentistry Ain Shams University Research Ethics committee and was approved before starting the research with number (566). Also the study was registered in clinical trial registration site (NCT).

Patient selection:

Inclusion Criteria:

- Patients who were indicated for soft tissue augmentation with free gingival graft for mucogingival surgery or for implant therapy.

Material and Method

- Age range (20-50) years.
- Good patient compliance with the plaque control instructions following initial therapy.

Exclusion criteria:

- Presence of systemic diseases which could influence the outcome of the therapy.
(American Society of Anesthesiologists I; ASA I)
- Smoker patients.
- Pregnant and lactating females.
- Vulnerable group of patients (prisoners, handicapped, decisionally impaired individuals).

Grouping Criteria:

The study consisted of three groups; the number of patient in each group was determined by sample size calculation based upon the results of *Yildirim et al. 2017*. Using alpha level of 0.05 (5%) and β level of 0.20 (20%) i.e. power = 80%; the estimated minimum required sample size was approximately 10 cases in each group. Patients were randomly selected using computer generated randomization (www.randomizer.org). Allocation concealment was achieved using a sealed coded opaque envelope containing treatment of the subject

Group I(10 patients):

Patients received platelet rich fibrin as a palatal dressing after free gingival graft harvesting.

Group II(10 patients):

Patients received hyaluronic acid* gel 3-4 times per day as a palatal dressing after free gingival graft harvesting.

Group III(10 patients) (Control group) :

Patients received gel foam as a palatal dressing after free gingival graft harvesting

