*Gengiegel 0.2% oral gel 20ml Riceerfarma Milano Italy.

III- Assessments:

1-Clinical parameters:

- Subjective assessment**

-Patients were asked to assess their pain sensation and bleeding at 1st, 3rd, 7th 14th, 21st and 30th days using the visual analogue scale (VAS). The visual analogue scale score by Price et al 1983 for pain ranged from 0 (no pain) to 10 (severe pain), while bleeding was scored as 0(not present) and 1(present) (***Price et al.1983***).

- Objective assessment**

-The Healing index scale by ***Landry et al.1988*** was used to assess the palatal wound healing, where in this index tissue color, response to palpation, presence of granulation tissue presence of suppuration and epithelization of the incision margin were recorded.

-The color of the palatal mucosa was assessed by comparing it to the adjacent and opposite side by taking pictures and using the image J program at 3rd, 7th, 14th, 21st and 30th days (***Pei-Nan et al.2012***).

- The thickness of the palatal mucosa was measured preoperative and 4 weeks postoperative by a graduated periodontal probe.

Material and Method

[figure not shown]

Fig (1): Palatal thickness measurements at 3 different points the middle of 1st, 2nd premolar and 1st molar 7mm from the gingival margin

IV-Surgical protocol:

A) Pre surgical procedures

Scaling and root planning was done; oral hygiene instructions was given to the patient to follow them.

B) Surgical procedures

Group 1:

1. Anesthesia (Articaine HCL 4% containing epinephrine at a concentration of 1:100,000)[†] was administrated at to the palate where a free gingival graft was harvested.
2. Just prior to surgery a 10 ml intravenous blood was obtained from the median antecubital vein of the patient in order to be divided into two 5 ml glass tubes[‡] without additives to be [§]centrifuged immediately at 2700 revolutions per minute for 12 minutes or in one 10 ml glass test tube without additives were centrifuged immediately at 3000 revolutions per minute for 10 minutes at room temperature.

[†] Artinibsa 4% cartouches de 1.8ml ,inibisa dental.

[‡] Dry Vacutube, Biocon®, Brazil

[§] PRF CENTRIFUGE (Duo machine), UNSPSC code 41100000 (Ostralos Ltd, New Zealand)

Material and Method

3. Coagulation started immediately and three parts quickly appear in the tube: a packed red blood cell at the bottom, acellular plasma at top and the PRF clot in between.

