4. The PRF clot was removed from the tube using sterile tweezers, separating it from the RBC base by using a lancet. It was compressed between two sterile glass slabs and wrapped within sterile gauze moistened with saline.
5. The thickness of the palatal tissue was measured at three different points; each point was located at the middle of 1st, 2nd premolar and 1st molar 7mm from the gingival margin.
6. Free gingival graft was harvested from the palate and its thickness was measured.
7. The PRF membrane was placed as a palatal dressing and fixed in place by X suture using 5-0 polypropylene**.

** Assut Sutures, non Absorbable (Polypropylene) 5-0 USP, braided violet coated 3/8 rev.cutt.17mm, AM trading, Switzerland

Group 2:

1. Anesthesia (Articaine HCL 4% containing epinephrine at a concentration of 1:100,000)^{††} was administrated at to the palate where a free gingival graft was harvested.
2. The thickness of the palatal tissue was measured at three different points; each point was located at the middle of 1st, 2nd premolar and 1st molar 7mm from the gingival margin.
3. Free gingival graft was harvested from the palate and its thickness was measured.
4. Gel foam was cut according to the graft's dimensions to act as a carrier for the hyaluronic acid^{‡‡}that was used as a palatal dressing.
5. Gel foam was fixed in place using X suture using §§5-0 polypropylene.

^{††}Artinibsa 4%cartouches de 1.8ml ,inibisa dental.

^{‡‡}Gengigel 0.2% oral gel 20ml Riceerfarma Milano Italy.

§§ Assut Sutures, non Absorbable (Polypropylene) 5-0 USP, braided violet coated 3/8 rev.cutt.17mm, AM trading, Switchezland

Group 3:

1. Anesthesia (Articaine HCL 4% containing epinephrine at a concentration of 1:100,000)^{***} was administrated at to the palate where a free gingival graft was harvested.
2. The thickness of the palatal tissue was measured at three different points; each point was located at the middle of 1st, 2nd premolar and 1st molar 7mm from the gingival margin.
3. Free gingival graft was harvested from the palate and its thickness was measured.
4. Gel foam was cut according to the graft's dimensions and used as a palatal dressing.
5. Gel foam was fixed in place using X suture using 5-0 polypropylene^{†††}.

^{***} Artinibsa 4% cartouches de 1.8ml ,inibisa dental.

^{†††} Assut Sutures, non Absorbable (Polypropylene) 5-0 USP, braided violet coated 3/8 rev.cutt.17mm, AM trading, Switchezland

Material and Method

V-Postoperative care:

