- Oral hygiene instructions was given , antibiotic (Augmentin^{†††} 1 gm every 12 hours, metronidazole^{§§§} 500 mg every 12 hours) , anti-inflammatory and analgesics(Brufen^{****} 400 every 12 hours) was prescribed for the patient and instructed to avoid brushing at the surgical site only rinsing with hot saline mouthwash.
- Patient was recalled for assessment and follow up, sutures was removed after 1 week.

^{†††} Augmentin 1gm,Medical union pharmaceuticals(MUP) Egypt under license from ,Glaxosmithkline

^{§§§}Flagyl 500 mg, sanofi Aventis Egypt under license of sanofi Aventis French

^{****} Brufen 400mg, Al kahira pharm. and chem.Ind.Co. under license from abbott laboratories

VI-Postoperative evaluation and assessment:

- Patients were asked to assess their pain sensation and bleeding at 1st, 3rd, 7th 14th, 21st and 30th days using the visual analogue scale (VAS). The visual analogue scale score by Price et al 1983 for pain ranged from 0 (no pain) to 10 (sever pain), while bleeding was scored as 0(not present) and 1(present).
- The Healing index scale by *Landry et al. 1988* was used to assess the palatal wound healing, where in this index tissue color, response to palpation, presence of granulation tissue presence of suppuration and epithelization of the incision margin were recorded.
- The color of the palatal mucosa was assessed by comparing it to the adjacent and opposite side by taking pictures and using the image J program at 3rd,7th, 14th, 21st and30th days.
- The thickness of the palatal mucosa was measured preoperative and 4 weeks postoperative by a graduated periodontal probe.

IV-Statistical analysis:

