Categorical data were presented as frequencies and percentages and were analyzed using chi square test. Numerical data were tested for normality using Shapiro-Wilk test and were presented as mean and standard deviation values. Parametric data were analyzed using one-way ANOVA followed by Tukey's post hoc test for intergroup comparisons and one-way repeated measures ANOVA followed by Bonferroni post hoc test for intragroup comparisons. Non-parametric data were analyzed using Kruskal-wallis test followed by pairwise comparisons utilizing Mann Whitney U test with Bonferroni correction for intergroup comparisons and Friedman's test of repeated measures followed by multiple pairwise comparisons utilizing Wilcoxon signed-rank test with Bonferroni correction for intragroup comparisons. The significance level was set at $p \leq 0.05$ within all tests. Statistical analysis was performed with IBM® SPSS® Statistics Version 26 for Windows.

® IBM Corporation, NY, USA.

®SPSS, Inc., an IBM Company.

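### Palatal thickness has a pre-treatment baseline, but the between-group tests ignore it; ANCOVA would be a cheap gain in precision if the pre/post correlation exceeds about 0.2

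*Protocol*

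**What the plan says.** Under VI-Postoperative evaluation and assessment, and in the same words under III- Assessments, the protocol says: "The thickness of the palatal mucosa was measured preoperative and 4 weeks postoperative by a graduated periodontal probe". The Fig (1) caption reads "Palatal thickness measurements at 3 different points". In the surgical steps for each of the three groups, "The thickness of the palatal tissue was measured at three different points" comes before the graft is harvested and before any dressing is placed.

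IV-Statistical analysis then sets the tests for all numerical outcomes together:

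- Between groups, normal data: "Parametric data were analyzed using one-way ANOVA followed by" Tukey's test.
- Between groups, otherwise: "Non-parametric data were analyzed using Kruskal-wallis test followed by pairwise comparisons utilizing Mann Whitney U test with Bonferroni correction".
- Across time, within a group: "one-way repeated measures ANOVA followed by Bonferroni post hoc test for intragroup comparisons", or Friedman and Wilcoxon tests if non-parametric.

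No covariate or baseline adjustment is named. The section does not say whether the between-group thickness test uses the 4-week value or the change. Since time points enter only the within-group tests, the natural reading is that the 4-week values are compared directly.

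On size, Grouping Criteria says "the estimated minimum required sample size was approximately 10 cases in each group", at alpha 0.05 and 80% power. It gives no effect size, SD or outcome for that calculation.

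**The concern.** A reading taken before treatment, on the same patient, site and instrument as the outcome, usually explains part of the outcome's variation. Leaving it out of the between-group comparison gives that precision away, and with 10 patients per group there is little to spare.

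Chance differences at baseline are large at this size. The unadjusted 4-week comparison carries the correlation times any such difference, and ANCOVA removes it. The standard error of the unadjusted test already allows for this, so the loss is one of efficiency and not of validity. It matters most for the pairwise comparisons, which show which dressings differ and have the lowest power.

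**Working it through.** **Inputs.** From the protocol: 3 groups, 10 patients each (N = 30), alpha 0.05, power 80%. Assumed: the pre/post correlation ρ, which the protocol does not give and which is shown over a range; bivariate normal data; a common slope.

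**The plan's own figure.** The sample size cannot be reproduced because no effect or SD is stated. It can only be inverted. For a three-group ANOVA with 10 per group, the noncentral F gives 80% power at f = 0.600. If one group is shifted and the other two are equal, the shift is f/√(2/9) = 0.600/0.4714 = 1.27 SD. This calibrates the comparison; the protocol does not say that it was sized on thickness.

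**Baseline imbalance.** The difference between two group means has SD √(2/10) = 0.447 in units of the outcome SD. P(|difference| > 0.5 SD) = 2[1 − Φ(0.5/0.447)] = 26% for a given pair. By simulation it is 50% for at least one of the three pairs. At ρ = 0.5, a 0.5 SD imbalance carries 0.5 × 0.5 = 0.25 SD into the unadjusted 4-week difference.

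**Break-even correlation.** The variance of an ANCOVA-adjusted pairwise difference, relative to the unadjusted one, is

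(1 − ρ²) × [1 + 1/(N − k − 2)] = (1 − ρ²) × (1 + 1/25) = 1.04 (1 − ρ²), with k = 3 groups.

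This equals 1 at ρ = √(1 − 1/1.04) = 0.196. Allowing for the lost error degree of freedom (26 against 27) moves it to 0.205. On simultaneous 95% interval width it is 0.207 with Tukey-Kramer and 0.312 with Bonferroni. At ρ = 0.5 the ratio is 0.78, equivalent to 10/0.78 = 12.8 patients per group. At ρ = 0.7 it is 0.53, or 18.9 per group.

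**Power at a shift of 1.27 SD** (40,000 simulated trials per ρ):

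| ρ | ANOVA, 4 weeks | ANCOVA | Tukey pair, 4 weeks | Tukey-Kramer pair, adjusted | Bonferroni pair, adjusted |
|---|---|---|---|---|---|
| 0 | 80.0% | 78.3% | 64.6% | 62.5% | 59.8% |
| 0.2 | 80.3% | 80.2% | 64.7% | 64.5% | 61.8% |
| 0.3 | 80.0% | 82.0% | 64.1% | 66.7% | 64.1% |
| 0.5 | 80.1% | 89.1% | 64.3% | 76.1% | 73.8% |
| 0.7 | 80.3% | 97.5% | 64.6% | 91.6% | 90.4% |
| 0.8 | 79.7% | 99.7% | 64.2% | 98.1% | 97.7% |

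The pair columns refer to one true difference of 1.27 SD. With no true effect, ANOVA and ANCOVA both reject in 4.9 to 5.2% of trials.

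**Rank branch** (20,000 trials per ρ). Kruskal-Wallis has about 76% power throughout, against Quade's rank ANCOVA at 76.5, 79.6, 85.7 and 95.0% for ρ = 0, 0.3, 0.5 and 0.7. For one pair with Bonferroni, Mann-Whitney has 54 to 55%, against 58.1, 62.2, 69.8 and 85.1% with Quade.

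**Other effect sizes.** Overall test, one group shifted, 60,000 trials per cell, ANOVA to ANCOVA:

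| Shift (SD) | ρ = 0.3 | ρ = 0.5 |
|---|---|---|
| 0.3 | 9 to 9% | 9 to 10% |
| 0.5 | 18 to 19% | 18 to 22% |
| 0.8 | 40 to 42% | 40 to 49% |
| 1.0 | 58 to 61% | 58 to 69% |
| 1.27 | 80 to 82% | 80 to 89% |
| 1.6 | 95 to 96% | 95 to 98% |

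**The case against.** The strongest reply is that nothing here is wrong. The planned tests are unbiased with correct type I error, and the statistical section is a general paragraph covering every numerical outcome; covariates per outcome are often left to a SAP. The first part is right and is why this ranks only as an optional improvement. The second does not remove the point, because the protocol names the between-group tests itself and they are unadjusted.

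A second reply is that the text does not exclude an ANOVA on change from baseline, which would already use the preoperative value. That is fair, and the 0.2 threshold applies only against the 4-week value. But a change score would not be the better choice. With equal pre and post SDs its power at the same effect is 49.2, 64.4, 79.8, 95.7 and 99.5% for ρ = 0, 0.3, 0.5, 0.7 and 0.8, never above ANCOVA. With a post SD 1.5 times the preoperative SD it is at most half a point above. At high ρ, however, the gain from replacing a change score is small.

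A third reply is that ρ is unknown and could be low, because a graft is cut from the same palate between the two readings and variable removal may weaken the correlation. This stands: the gain is conditional. At ρ = 0.3 it is no more than about 2 points on the overall test at any effect size tried, and at ρ = 0.5 it ranges from about 1 to 11 points.

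Finally, the text is in the past tense and reports the enrolled sex split, so the change may come too late to be prespecified. That limits its standing, as set out in the fix.

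**Conclusion.** The point holds as a low-priority improvement. Thickness has a baseline taken before treatment, the protocol's between-group tests make no use of it on the natural reading, and ANCOVA is the more precise analysis once ρ exceeds about 0.2 with 10 patients per group.

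The trade is lopsided. If ρ is near zero, ANCOVA loses about 2 points of power. At ρ = 0.5, for an effect of 1.27 SD, it gains about 9 points on the overall test and 12 on a pairwise comparison. The pairwise interval half-width falls from 1.11 to 0.98 SD.

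This rests on an assumed range for ρ, roughly normal data, a common slope, and the 4-week value being the variable compared. It does not put the validity of the planned tests in doubt, and it concerns one of five outcomes, none of them named primary.

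**What to change.** In IV-Statistical analysis, state that 4-week palatal thickness is compared between groups by ANCOVA, with group as factor and preoperative thickness as covariate. Use one value per patient at each visit: the mean of the three points in Fig (1). Follow it with Tukey-Kramer comparisons of the adjusted means, which keeps the post hoc procedure already chosen. Bonferroni is acceptable but gives up 0 to 3 points of power. If residuals are clearly non-normal, use Quade's rank ANCOVA with Bonferroni pairwise comparisons.

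The cost is about two sentences and no new data. The analysis spends one of 27 error degrees of freedom and assumes a common slope across groups. At ρ near zero it loses about 2 points of power, or about 5 on the pairwise comparisons if Bonferroni is used (64.6 − 59.8 = 4.8). If outcome data have already been seen, present the adjusted result as a supporting analysis added later, beside the unadjusted one.

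### Graft thickness is measured in every patient but has no role in the stated comparison of 4-week palatal thickness, which mainly costs precision

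*Protocol*

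**What the plan says.** Palatal thickness is one of the objective assessments (Protocol, III- Assessments and VI-Postoperative evaluation and assessment): "The thickness of the palatal mucosa was measured preoperative and 4 weeks postoperative by a graduated periodontal probe". Neither section says whether groups are compared on the 4-week value or on the change.

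Under IV-Surgical protocol the order is the same in each group. The palate is probed at three points, where "each point was located at the middle of 1st, 2nd premolar and 1st molar 7mm from the gingival margin". Then "Free gingival graft was harvested from the palate and its thickness was measured". The dressing follows. No target depth, graft size or harvest position is given. Grafts evidently differ in size, since in Group 3 "Gel foam was cut according to the graft's dimensions and used as a palatal dressing". Graft thickness is not mentioned again.

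The Protocol's section IV-Statistical analysis sets the between-group method for numerical data: "Parametric data were analyzed using one-way ANOVA followed by Tukey's post hoc test for intergroup comparisons", with Kruskal-Wallis as the non-parametric counterpart. It names no covariate.

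**The concern.** At a point inside the wound, thickness at 4 weeks equals preoperative thickness, minus depth removed, plus tissue regained. A dressing placed after harvest can act only on the last term. The unadjusted 4-week value carries variation from the first two terms. The change from baseline removes the first but keeps some or all of the second. Both nuisance quantities are measured before the dressing goes on, so they are legitimate adjustment variables that the stated analysis leaves unused. With 10 patients per arm, that can decide whether a real difference in thickness is detectable.

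**Working it through.** **The plan's own figure.** Grouping Criteria gives about 10 per group at alpha 0.05 and 80% power, but no effect size, SD or endpoint, so it cannot be reproduced. Inverted, 10 per group implies a standardised difference of 1.25 (normal approximation) or 1.32 (two-sample t-test), or ANOVA f = 0.60. It says nothing about thickness in particular.

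**Assumptions, none from the documents.** SD of regain 0.3 mm, of graft thickness 0.3 mm, of preoperative thickness 0.5 mm, all independent; a true effect of 0.4 mm in one arm; three groups of 10. Let r be the fraction of removed depth that refills without any dressing effect. The documents give no r, so the whole range is shown.

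**Within-group SD of each candidate outcome.**
- 4-week thickness: √(0.5² + (1−r)²·0.3² + 0.3²)
- Change from baseline: √((1−r)²·0.3² + 0.3²)
- Subtraction score, 4-week − (preoperative − graft): √(r²·0.3² + 0.3²)

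The one-way ANOVA noncentrality is 10 × (2/3) × 0.4² / SD² = 1.067/SD², with 2 and 27 degrees of freedom. For change at r = 0, 1.067/0.18 = 5.93, which gives 53% power. At r = 1, 1.067/0.09 = 11.85, which gives 84%.

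| r | 4-week value: SD, power | Change: SD, power | Subtraction: SD, power | ANCOVA, both covariates |
|---|---|---|---|---|
| 0 | 0.656, 24–25% | 0.424, 53% | 0.300, 84% | about 80% |
| 0.5 | 0.602, 29% | 0.335, 74–75% | 0.335, 74–75% | about 80% |
| 0.8 | 0.586, 30% | 0.306, 82% | 0.384, 62% | about 80% |
| 1 | 0.583, 30% | 0.300, 84% | 0.424, 53% | about 80% |

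The ANCOVA column is simulated. Where two figures stand, simulation and the noncentral F differ by a point. ANCOVA is stable across r because it estimates the slope on depth. Change and subtraction each fix that slope in advance.

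**Chance differences in depth.** The SE of the difference in mean graft thickness between two arms is 0.3 × √(2/10) = 0.134 mm, so the 95% range is ±0.26 mm. The 95th percentile of the largest gap among three arms is 0.31 mm. In simulation with no systematic gap, the unadjusted tests keep about 5% type I error.

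**A systematic difference in depth.** Suppose one arm is cut 0.5 mm deeper and no dressing has any effect. The false-positive rate on change is 62% at r = 0.2, 35% at r = 0.5 and 10% at r = 0.8. With both covariates it is about 5%. The subtraction score reaches 61% at r = 0.8. A gap can also hide a benefit: at r = 0.2 the deeper arm loses (1 − 0.2) × 0.5 = 0.4 mm, which cancels a true 0.4 mm gain. Power is then 4–5% unadjusted, against 60% when change is adjusted for graft depth.

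**The case against.** A reader might infer that harvest differences will pass for a dressing effect. The documents do not support that. Allocation is randomised and concealed in opaque envelopes, chance differences in depth are already part of the ANOVA error term, and type I error stays near 5%. The 0.5 mm gap above is imposed, and it exceeds the 0.31 mm that chance alone would rarely pass. What remains is that a systematic gap is not excluded. Harvest depth is not standardised, the time of opening the envelope is not stated, and in Group 1 "Just prior to surgery a 10 ml intravenous blood was obtained from the median antecubital vein of the patient", so the arm can be known before the graft is cut. This is an opening for bias, not evidence of it.

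A reader might also conclude that the three points lie partly on unoperated mucosa and dilute the result. That too goes beyond the text. The figure captioned "Palatal thickness measurements at 3 different points the middle of 1st, 2nd premolar and 1st molar 7mm from the gingival margin" is not shown in the copy reviewed, no graft length is given, and no rule for averaging the points is stated. The inclusion criterion, "soft tissue augmentation with free gingival graft for mucogingival surgery or for implant therapy", says nothing about graft size. If the points were averaged and one or two lay outside the wound, 2/3 or 1/3 of an effect would remain, but the protocol shows neither condition. What stands is that the points are not stated to lie within the wound.

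Finally, covariates are often left to an analysis plan, and one may exist. That is fair as far as it goes. But this protocol has its own statistical section, and that section fixes an unadjusted comparison. Thickness is one of several assessments and is not named primary, which limits the weight of the point.

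**Conclusion.** The point holds as a matter of efficiency. The stated between-group analysis leaves measured pre-dressing variation in the error of the thickness comparison. Under the assumed SDs, adjusting for preoperative and graft thickness gives about 80% power, against 24–30% for unadjusted 4-week thickness. Against change (53–84%), the gain runs from about 27 points with no refill to a loss of about 2–4 points when refill is near complete. These sizes rest wholly on assumed SDs and on an unknown refill fraction. Bias is conditional on a systematic difference in harvest depth between arms. The relation of the probing points to the wound is a secondary gap in the description. This is a worthwhile improvement to one outcome and does not invalidate the trial.

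**What to change.** State that 4-week palatal thickness is compared between groups by ANCOVA with preoperative thickness and measured graft thickness as covariates. Do not replace this with the subtraction score. It is not equivalent, and it adds noise or bias when deeper wounds refill more.

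This needs no new measurement, visit or patient. It uses two degrees of freedom (error 27 to 25), and probe error in the graft measurement weakens the adjustment. Because the values are already collected, it remains possible if surgery is complete, as the past-tense text and final patient counts suggest.

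Secondarily, state how the three points relate to the graft outline. Where it can still be recorded, note which points fall inside it and run the comparison on those points, averaged per patient. That costs one tick per point at surgery, and some patients would contribute fewer than three points. It cannot be recovered later if it was not recorded.

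### Is the chi-square test unsafe for yes/no bleeding with 10 patients per arm?

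*Protocol*

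**What the plan says.** Under IV-Statistical analysis the protocol gives one rule for categorical outcomes: "Categorical data were presented as frequencies and percentages and were analyzed using chi square test". It does not say which form of chi-square is meant, and it names no alternative for small counts. The threshold is p ≤ 0.05 for all tests.

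The outcome affected is bleeding. Under III- Assessments and again under VI-Postoperative evaluation and assessment, "bleeding was scored as 0(not present) and 1(present"), and the schedule is fixed: "Patients were asked to assess their pain sensation and bleeding at 1st, 3rd, 7th 14th, 21st and 30th days". That is six set days.

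On size, Grouping Criteria states that "The study consisted of three groups" and that "the estimated minimum required sample size was approximately 10 cases in each group". Sample selection and assignment opens with "Thirty patients (16 females and 14 males"). The document gives no expected bleeding rate and does not call bleeding a primary outcome.

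**The concern.** Chi-square p-values rest on a large-sample approximation. The usual rule of thumb asks for expected counts of at least 5, and with 10 patients per arm that rule fails for almost every possible bleeding total. For numerical data the same section checks normality and provides non-parametric tests as a fallback. For categorical data it provides neither a check nor a fallback.

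If the approximation were poor, a bleeding result near 0.05 could be reported as significant when an exact test would say otherwise. The clearest case is a day with three bleeders, all in one arm: chi-square gives p = 0.036, the exact test 0.089. At stake would be a false claim that one dressing reduces or increases bleeding.

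**Working it through.** **Inputs.** Three arms of 10 (Grouping Criteria); bleeding 0/1 on each assessment day (III- Assessments); threshold p ≤ 0.05 (IV-Statistical analysis). All 30 patients are taken as assessed. Bleeding rates are assumptions, because the document gives none. The protocol has no figure of its own on this point to reproduce.

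**Step 1: expected counts.** With s bleeders among 30, each arm expects s/3 bleeders and 10 − s/3 non-bleeders. Both reach 5 only if s = 15. At the other 28 totals from 1 to 29, exactly 3 of the 6 expected counts are below 5. The sex split also falls short: 14/3 = 4.67 expected males per arm. The premise of the concern is therefore correct.

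**Step 2: where verdicts change.** There are 11³ = 1331 ordered tables, or 286 if the order of the arms is ignored. For each, Pearson chi-square (2 degrees of freedom) was compared with Fisher-Freeman-Halton.

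Example 0/0/3: expected counts are 1 and 9 per arm, so chi-square = (1 + 1 + 4)/1 + (1 + 1 + 4)/9 = 6.67 and p = 0.036. The exact p is 3 × C(10,3)/C(30,3) = 360/4060 = 0.089.

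| Bleeders per arm | Total (mirror) | Chi-square p | Exact p |
|---|---|---|---|
| 0/0/3 | 3 (27) | 0.036 | 0.089 |
| 0/1/4 | 5 (25) | 0.044 | 0.094 |
| 0/3/5 | 8 (22) | 0.039 | 0.053 |
| 1/2/6 | 9 (21) | 0.036 | 0.077 |

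With mirror images that is 8 of 286 patterns, all significant by chi-square only. At the other 29 − 8 = 21 totals, including every total from 10 to 20, no verdict changes. Yet expected counts are below 5 at 20 of those 21. The rule of thumb therefore does not identify where the choice of test matters. At the sex split's totals (14 and 16) nothing changes.

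**Step 3: does chi-square hold its level?** Probability of p ≤ 0.05 when all arms share one bleeding rate:

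| Common rate | Chi-square | Fisher-Freeman-Halton | Mid-p |
|---|---|---|---|
| 5% | 1.4% | 0.1% | 1.4% |
| 10% | 3.7% | 0.7% | 3.7% |
| 20% | 5.0% | 2.2% | 4.8% |
| 30% | 4.7% | 3.2% | 4.4% |
| 50% | 4.2% | 4.1% | 4.7% |

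Over all common rates the maximum is 5.01% for chi-square, 4.07% for Fisher-Freeman-Halton and 4.83% for mid-p. Chi-square exceeds its level by at most 0.01 percentage points.

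**Step 4: what the disagreement means when arms differ.** Because every change runs from significant to not significant, the disagreement rate equals the power lost by moving to the exact test.

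- Assumed rates 5/5/40%: 59.5 − 41.5 = 18.0 points.
- Assumed rates 10/10/50%: 58.5 − 47.4 = 11.1 points.
- Assumed rates 20/20/60%: 5.7 points; 30/30/70%: 1.3; 20/50/80%: 0.3.

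In all of these the arms truly differ, so chi-square reaches the right answer more often.

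**Step 5: mid-p as an alternative.** It changes the chi-square verdict in 1/2/6 (0.036 to 0.058) and 1/5/6 (0.054 to 0.047) and their mirrors, 4 of 286 patterns. Both tests call 153 patterns significant, and power at 5/5/40% is almost the same (58.9% against 59.5%).

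**The case for a change.** The strongest case against chi-square is conditional on the observed total. Given 3 bleeders, its false-positive rate is 8.9%; given 5 it is 9.4%, given 9 it is 7.7%, and given 8 it is 5.3%. Fisher-Freeman-Halton stays at or below 5% at every total. The figures are right, and a statistician who insists on conditional inference may prefer the exact test. But that is a choice of framework, and here it costs power when bleeding is rare. Mid-p does not settle the matter, as it has the same 8.9% and 9.4% at totals 3 and 5.

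A second argument is that the words chi-square do not fix one statistic. The likelihood-ratio form disagrees with Pearson in 12 of 286 patterns (0/4/4: 0.020 against 0.065), and its size reaches 8.7% at a common rate of 25%. That would matter if it were used. The unqualified name ordinarily means the Pearson test, however, and nothing in the protocol points to the other form. Settling the version is routine detail for a statistical analysis plan, so its absence from this protocol is not a fault.

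A third argument is that the section fixes a test and gives no fallback, so the choice is made here and is not deferred. That is true as a reading of the text, but a fixed choice is a defect only if it misleads, and the enumeration shows that it does not.

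**Conclusion.** The concern does not hold. The expected counts are small, as claimed, but the consequence feared from small counts does not follow: Pearson chi-square in three arms of 10 has a false-positive rate of at most 5.01%. Verdicts differ from the exact test in 8 of 286 patterns, confined to totals 3, 5, 8, 9 and their mirrors. Replacing the test would either cost power (18.0 points at assumed rates of 5/5/40%, 0.3 at 20/50/80%) or, with mid-p, change almost nothing.

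This rests on reading chi-square as Pearson's test, on all 30 patients being assessed on each day, and on judging false positives over all possible totals and not within each total. The maximum of 5.01% needs no assumed bleeding rate; the power figures do. Bleeding is not called primary, so even the few borderline tables bear little on the trial's conclusions.
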